Study 002: Dose ranging study of carbidopa-levodopa

Study Design: Prospective, open-label, escalating dose

PI: [name], PhD

Protocol Version 4

Date: June 24, 2017

IND Number: 132078

ClinicalTrials.gov identifier: NCT 03023059

Objectives:

1. To determine whether L-DOPA-carbidopa supplementation can improve visual function, within 30-90 days, in patients with neovascular AMD (nAMD), by evaluating best-corrected visual acuity (BCVA).
2. To determine whether L-DOPA-carbidopa supplementation can improve the anatomic findings on optical coherence tomography (OCT), within 30-90 days, in patients with nAMD.
3. To evaluate the relative benefits of carbidopa-levodopa 25-100 mg, one tablet QHS, one tablet TID, and two tablets TID.
4. To determine whether L-DOPA-carbidopa supplementation in escalating daily doses is well tolerated in our target group of patients with nAMD in one eye.
5. To evaluate the effect of carbidopa-levodopa on anti-VEGF injections.

Inclusion criteria

- A diagnosis of AMD with choroidal neovascularization (CNV) in one eye.
 - Not previously treated with anti-VEGF injections; or
 - On anti-VEGF injections for at least 3 months, and meets criteria for a repeat injection; or
 - Patients, who have completed Study 001, may enter this trial at the point of initiation of the month of treatment with the dose of carbidopa-levodopa, that they received in Study 001.
- Normal or dry AMD of any grade in the fellow eye.
- Age 50-85 years.

- Willingness to maintain AREDS vitamin supplements throughout the study or remain off these supplements for the duration of the study, if not taking them prior to the study.
- Written informed consent at baseline.

Exclusion criteria:

- Any current use of L-DOPA containing medication or dopamine agonist medication, or any planned use of any of these agents, except for study medication, during the study.
- Concurrent use of monoamine oxidase (MAO) inhibitors.
- Any eye condition, disease, or history of trauma in either eye, which can impair vision, except cataract or cataract surgery.
- BCVA worse than 20/60 in the fellow eye.
- nAMD in the fellow eye.
- Neurologic conditions which can impair vision.
- Parkinson's disease.
- Significant orthostatic hypotension, defined as a drop in systolic blood pressure, immediately upon changing from the supine to standing position, of >19 mmHg, or a symptomatic drop in systolic blood pressure, immediately upon changing from the supine to standing position.
- Significant ECG abnormalities, as judged by the Investigator.
- Estimated glomerular filtration rate (eGFR) <20 ml/min.
- Liver enzymes >3 X the upper limit of normal.
- HbA₁C >9.0.
- Any other significant lab abnormalities, as judged by the Investigator.
- Women of childbearing potential.

- Known retinal hemorrhage.
- Subjects who are not fluent in English.

Treatments: Patients will receive open label carbidopa-levodopa 25-100 mg one tablet QHS for one month, followed by one tablet TID, in the morning, with supper and at bedtime for one month, followed by two tablets TID, in the morning, with supper and at bedtime for one month (100-600 mg of levodopa daily). This is the equivalent of very low to moderate doses of carbidopa-levodopa in patients with Parkinson's disease (daily dose of levodopa 200-800 mg). Patients entering this study after completing Study 001 will receive one month of the dose that he or she received in Study 001, and one month each of any doses higher than the dose that he or she received in Study 001.

Examples:

1. If the patient received carbidopa-levodopa 25-100 mg once daily in Study 001, he or she will receive one month of treatment with each of the 3 daily doses of carbidopa-levodopa.
2. If the patient received carbidopa-levodopa 25-100 mg TID in Study 001, he or she will receive one month of carbidopa-levodopa 25-100 mg TID, followed by one month of carbidopa-levodopa 25-100 mg, 2 tablets TID.

Each patient will receive an injection of anti-VEGF medication on the day carbidopa-levodopa dosing begins in this study. Each patient will be evaluated at monthly (25-35 day) intervals and in conjunction be evaluated by the referring Retina Specialist who will assess whether the patient requires an anti-VEGF injection, based on clinical practice standard of care.

What are the risks of taking carbidopa-levodopa?

- Body as a whole: chest pain, feeling weak and fatigued.

- Cardiovascular: irregular heartbeat, low blood pressure, low blood pressure immediately upon standing, high blood pressure, fainting, vein inflammation and palpitations.
- Gastrointestinal: dark saliva, ulcers, loss of appetite, nausea, vomiting, diarrhea, constipation, heartburn, dry mouth, altered taste and gastrointestinal bleeding.
- Hematologic: anemia, low white blood cells, low platelets.
- Hypersensitivity: skin rash, itching, face or throat swelling.
- Musculoskeletal: back pain, shoulder pain, muscle pain.
- Nervous system/Psychiatric: delusions, hallucinations, confusion, agitation, dizziness, sleepiness, abnormal dreams, insomnia, abnormal sensations, headache, depression, abnormal movements, mental difficulties, urge to gamble, increased sexual desire, problems with impulse control.
- Respiratory: shortness of breath, upper respiratory infection.
- Skin: Rash, increased sweating, hair loss, dark sweat.
- Urogenital: urinary tract infection, urinary frequency, dark urine.

Dealing with Adverse Events: Study Participants will be asked about any adverse events at each visit, and asked to tell the study doctor or study staff right away if they have any side effects, or if they have any other problems with their health or the way they feel during the study, regardless of whether or not they think these problems are related to the study drug. The answers will be recorded in the source documents. For minor and easily tolerated events, the participants will continue in the study, unless they request to be withdrawn from the study. For serious or poorly tolerated events, the patient will be withdrawn from the study. Appropriate medical care will be instituted for any serious adverse events (SAEs).

Number of subjects: 52 completed

Recruiting: In order to enhance recruiting, ophthalmology technicians in the offices of the Retina Specialists will be asked to identify patients who meet the criteria for the study and bring them to the attention of the Retina Specialist, who will decide whether or not to refer the patient. If the patient is referred and meets the criteria for the study, the technician will be paid \$25.

Duration: Up to 105 days of treatment.

Measurements and Activities:

- Written informed consent at Baseline.
- Ophthalmic history and comprehensive eye examination; including visual acuity, wearing any prescription lenses, using an EDTRS chart, in both eyes prior to randomization, and ophthalmoscopic examination, and OCT.
- Repeat assessment of visual acuity using an EDTRS chart, ophthalmoscopic examination, and OCT at monthly visits.
- Subjective Vision Questionnaire at monthly visits.
- Demographics at Baseline.
- Medical History, Vital Signs and Physical Examination at Baseline.
- ECG, CBC, Chem 20 and HbA₁C at Baseline.
- Dispense study medication at visits, 1,2 and 3.
- Pill count at monthly visits.
- Non-directed assessment of adverse events at each visit, including classification as to severity, seriousness and body system.
- Concomitant medications at each visit.
- If a patient had the baseline evaluation in Study 001, that will be used as the baseline evaluation for this study.

Criteria for repeat anti-VEGF injections:

This will be based on monthly evaluation of: BCVA (decrease of 5 letters from previous visit); increased central macular thickness (compared to normal and previous visit as measured by OCT; new blood (hemorrhage) on direct retinal examination; or subjective decrease in vision. If any of these criteria are met, or if, in the opinion of the Retina Specialist, the patient requires anti-VEGF therapy, the patient will have an anti-VEGF intraocular injection. If none of these criteria are met at visits 2, 3 or 4, with patient agreement, anti-VEGF injection will not be done, and the patient will be reevaluated in 1 month.

Result sharing with subjects:

After the conclusion of the study, patients will be notified of the results, regarding safety, tolerability and vision-related outcomes.

Table of Study Activities by Visit

	Visit 1 (Baseline)	Visit 2	Visit 3	Visit 4
		25-35 Days	25-35 Days	25-35 Days
Informed Consent	X			X
Demographics	X			
Medical History	X			
Concomitant Medications	X	X	X	X
Adverse Event Assessment	X	X	X	X
Physical and Vital Signs	X			
Vital Signs		X	X	X
ECG	X			
CBC, Chem 20, HbA ₁ C	X			
Subjective Vision Test	X	X	X	X
Retinal Exam	X	X	X	X
BCVA (ETDRS Protocol)	X	X	X	X
SD-OCT Scan	X	X	X	X
Dispense Medication	X	X	X	X
Pill Count		X	X	X

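### No postural blood pressure reading is required after dosing starts, although entry is decided on one and low standing pressure is a listed drug risk

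*Protocol*

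**What the plan says.** Objective 4 is "To determine whether L-DOPA-carbidopa supplementation in escalating daily doses is well tolerated in our target group of patients with nAMD in one eye".

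Under Treatments, the daily dose goes up in monthly steps over a range of "100-600 mg of levodopa daily". Some patients join part-way up: those who took the TID dose in Study 001 start here with a month at that dose and then move to the highest.

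The Exclusion criteria include "Significant orthostatic hypotension, defined as a drop in systolic blood pressure" of more than 19 mmHg on moving from lying to standing, or a drop with symptoms on the same change of position. The section on the risks of carbidopa-levodopa lists, under cardiovascular, "low blood pressure, low blood pressure immediately upon standing, high blood pressure, fainting".

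Two places set out what is measured and when:

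- The list under Measurements and Activities has "Medical History, Vital Signs and Physical Examination at Baseline". It names acuity, OCT, the vision questionnaire and the pill count as monthly. Vital signs are not among the monthly items.
- The Table of Study Activities by Visit has a combined physical and vital signs row marked at Visit 1, and a separate vital signs row marked at Visits 2, 3 and 4. Neither row gives a body position.

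Adverse events are assessed at each visit by non-directed enquiry, and participants are asked to report problems as they arise (Dealing with Adverse Events).

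**The concern.** The entry criterion can be applied only by comparing supine with standing pressure, so the protocol implies that reading once, before treatment. It then raises the dose of a drug for which it lists low standing pressure as a risk, and asks for no comparable reading at any dose. Non-directed questioning picks up what the patient notices. A systolic drop of more than 19 mmHg without symptoms counts as significant at entry, yet no required procedure would find it at Visits 2 to 4.

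What is at stake is the content of objective 4 in patients aged 50 to 85. This is not a matter the statistical analysis plan can settle, because an analysis plan cannot summarise readings that were never taken.

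**Working it through.** **Dose range (Treatments).** Daily levodopa = tablets per dose x doses per day x 100 mg.

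- Step 1: 1 x 1 x 100 = 100 mg
- Step 2: 1 x 3 x 100 = 300 mg
- Step 3: 2 x 3 x 100 = 600 mg

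This reproduces the stated range of 100 to 600 mg. The rise is 600/100 = 6-fold for patients who start at the lowest dose, and 600/300 = 2-fold for Study 001 entrants who start on TID.

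**What is required after baseline.**

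| Source | Visits with vital signs after baseline | Posture stated | Postural readings required |
|---|---|---|---|
| Measurements and Activities (list) | 0 of 3 | no | 0 of 3 |
| Table of Study Activities by Visit | 3 of 3 | no | 0 of 3 |

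The two sources differ on whether vital signs are scheduled, and agree in not requiring a supine-to-standing comparison. A site working from the list alone would take no follow-up reading. A site working from the table could take one in any position.

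**What could go unrecorded.** The protocol gives no incidence of a postural drop, so this is an illustration on assumptions. Let n = 52 (Number of subjects, completed), p = share of patients who develop a drop of more than 19 mmHg (assumed 5 to 20%), and s = share of those drops that reach the record through adverse event enquiry (assumed 0 to 100%).

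- Expected cases = n x p: 52 x 0.05 = 2.6; 52 x 0.10 = 5.2; 52 x 0.20 = 10.4.
- Expected unrecorded = n x p x (1 - s):

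| p | s = 0% | s = 25% | s = 50% | s = 100% |
|---|---|---|---|---|
| 5% | 2.6 | 1.95 | 1.3 | 0 |
| 10% | 5.2 | 3.9 | 2.6 | 0 |
| 20% | 10.4 | 7.8 | 5.2 | 0 |

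- Probability that adverse event data show at least one case = 1 - (1 - p x s)^52. With s = 25% this is 0.48 at p = 5%, 0.73 at p = 10% and 0.93 at p = 20%.

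The result runs from 0 to about 10 patients depending wholly on p and s. It shows how the gap works and does not estimate its size.

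**The case against.** The strongest reply is that the schedule is incomplete rather than faulty. The list omits follow-up vital signs without excluding them, and the table gives them their own row at Visits 2 to 4, so the natural reading is that they are taken. Posture is not named at Visit 1 either. If the label there covers the supine and standing readings that the entry criterion needs, the same label later may cover them too. Symptomatic drops, dizziness and fainting can come out through adverse event enquiry at every visit, and an asymptomatic reading is the least direct evidence on tolerability.

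Most of this stands, and it rules out stronger readings that a reader might infer:

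- *That no vital signs are taken after baseline.* The table points the other way.
- *That the risk is dose-related.* The protocol lists it without tying it to dose.
- *That this is the only safety measure with an objective limit.* The Exclusion criteria also set numeric limits for eGFR, liver enzymes and HbA1c.
- *That every patient has a sixfold rise.* Study 001 entrants on TID have a twofold rise.
- *That postural drops will be missed.* Only those without symptoms or not reported are exposed, and a site may choose to take the readings.

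The reply does not remove the gap. A measurement that sites may or may not infer from an unqualified label is not a required one, and it cannot be relied on to be collected in the same way at each dose.

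**Conclusion.** The point holds as a gap in measurement together with a mismatch between list and table. After dosing starts, 0 of 3 follow-up visits require the comparison on which entry was decided, whichever source is followed. An asymptomatic drop meeting the entry definition could therefore go unrecorded at any of the three doses. Objective 4 would then rest, for this risk, on what patients report and on readings in an unstated position.

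The number of patients affected cannot be had from the documents. A reader might take a figure such as 3 to 5 of 52 from an assumed rate of 5 to 10% with none reported, but that returns only the assumption. The tolerability conclusion is limited, not invalidated. The change is worth making because it is cheap and the data cannot be recovered later.

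**What to change.** 1. Make the list under Measurements and Activities agree with the visit table, so that both show vital signs at Visits 2, 3 and 4.
2. State in both places that vital signs at Visit 1 and at Visits 2 to 4 include supine and immediate standing systolic pressure, measured as for the entry criterion. The postural change can then be summarised by dose step under objective 4.
3. Because a Study 001 baseline evaluation may serve as the baseline here, say which reading is the reference for those entrants.

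The cost is two cuff readings and a few minutes per visit, at visits where the table already schedules vital signs, and one more table in the report. What to do clinically when a drop is found is left to the clinical team.

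### Objective 3 promises the relative benefits of three doses, but for new entrants dose is the same variable as month, and Study 001 rollovers separate the two only under doubtful cross-cohort assumptions

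*Protocol*

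**What the plan says.** The third item of the protocol's Objectives is "To evaluate the relative benefits of carbidopa-levodopa 25-100 mg, one tablet QHS, one tablet TID, and two tablets TID".

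The Treatments section sets the order. "Patients will receive open label carbidopa-levodopa 25-100 mg one tablet QHS for one month, followed by one tablet TID", and the third month is two tablets TID. It describes no other order, no parallel dose group and no washout.

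Patients who completed Study 001 start at their Study 001 dose and then take "one month each of any doses higher than the dose that he or she received in Study 001". Two cases are illustrated:
- Once-daily rollovers: "he or she will receive one month of treatment with each of the 3 daily doses of carbidopa-levodopa".
- TID rollovers: "one month of carbidopa-levodopa 25-100 mg TID, followed by one month of carbidopa-levodopa 25-100 mg, 2 tablets TID".

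Three further statements bear on the comparison:
- Treatments: "Each patient will receive an injection of anti-VEGF medication on the day carbidopa-levodopa dosing begins in this study". Later injections depend on monthly criteria or the Retina Specialist's opinion (Criteria for repeat anti-VEGF injections).
- Measurements and Activities: "If a patient had the baseline evaluation in Study 001, that will be used as the baseline evaluation for this study".
- Sample size: "Number of subjects: 52 completed". No split between new entrants and rollovers is given.

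**The concern.** A relative benefit is a contrast between doses. For a new entrant, Visit 2 always closes the lowest-dose month, Visit 3 the middle and Visit 4 the highest. Any change with time therefore appears as a difference between doses.

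Time is not neutral in this trial. Everyone is injected on the first dosing day, and later injections respond to the patient's course. Patients never treated with anti-VEGF are eligible alongside those on it for at least 3 months. A slow or cumulative response to injections would look like a benefit of the highest dose. Waning after the first injection would look like a benefit of the lowest. The net direction is unknown.

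The risk is that step-by-step results of an escalation are read as a dose ranking for vision and anatomy, when they describe only the cumulative response along one path.

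**Working it through.** The question is whether the dose differences can be identified, so the check is the rank of the design matrix. A dose difference is estimable only if adding it as an extra row leaves the rank unchanged.

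**Inputs from the protocol.** 52 completers. Dose sequence 1-2-3 for new entrants and once-daily rollovers, 2-3 for TID rollovers, where 1, 2 and 3 are the lowest, middle and highest dose. Baseline counts as dose 0. **Assumed:** the splits between cohorts.

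**New entrants only, free month effects.**
- Visits 2 to 4: 52 patient + 2 visit + 2 dose terms = 56 parameters; rank 54.
- With Visit 1: 52 + 3 + 3 = 58 parameters; rank 55.
- None of the three pairwise dose differences is estimable in either case.

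In terms of mean change from baseline, new entrants give m1+d1, m2+d2 and m3+d3 (m = month effect, d = dose effect). Each dose effect occurs only in a sum with its own month effect. With no dose effect at all and a steady change of *t* letters a month, the apparent highest-minus-lowest difference is 2*t*: 2, 4 or 6 letters for *t* = 1, 2 or 3 (illustrative values). At *t* = 2.5 it is 5 letters, which is the BCVA loss that the protocol lists as a criterion for another injection.

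**Adding rollovers, Visit 1 included.**

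| Cohorts (assumed split) | Month profiles | Rank / parameters | Dose differences estimable |
|---|---|---|---|
| 42 new + 10 once-daily | one, shared | 55 / 58 | none |
| 42 new + 10 TID | one, shared | 57 / 58 | all three |
| 42 new + 10 TID | one per cohort | 57 / 60 | none |
| 32 new + 10 once-daily + 10 TID | one, shared | 57 / 58 | all three |
| same | shared, plus one rollover offset | 58 / 59 | all three |
| same | one for new entrants, one for rollovers | 60 / 61 | all three |
| same | one per cohort | 60 / 63 (52 + 3 + 3 + 2 + 3) | none |

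The ranks for the three-cohort mix are the same at 42+5+5 and 50+1+1. Rank says nothing about precision, which would be poor with so few rollovers.

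**Why the 60 / 61 row works.** If the two rollover groups share a profile r, their mean changes are r1+d1, r2+d2, r3+d3 (once-daily) and r1+d2, r2+d3 (TID). TID minus once-daily is then d2−d1 at Visit 2 and d3−d2 at Visit 3, and the sum of the two is d3−d1. New entrants contribute nothing to these differences. There are 3+3+2 = 8 mean changes for 60−52 = 8 estimable quantities, so nothing is left over to test the shared profile.

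**The case against.** The strongest reply has four parts.

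**Rollovers can break the aliasing.** This is correct, and a reader might wrongly infer that they never can. If both illustrated rollover types enrol, the two groups need only share a month profile with each other; they need not share the new entrants' profile. A common offset, for example from the reused Study 001 baseline, can then be fitted as well. Once-daily rollovers add nothing alone but do help beside TID rollovers. A shared profile that leaves no degrees of freedom to test it, and a cohort offset that passes straight into the dose differences, are features of new entrants plus TID rollovers only. They must not be stated for the trial as a whole.

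**The rollover groups may have been randomised in Study 001.** The protocol does not say how Study 001 assigned dose, so it cannot be asserted that they were not. New entrants and rollovers, at least, are not randomised against each other. The single mention of randomization, under Measurements and Activities, has no procedure attached and does not help.

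**Some analysis could separate dose from time.** In new entrants alone, a straight-line trend in actual days, using the 25-35 day visit window, with free dose effects gives 56 of 56 (simulated visit days). Linear time with linear dose gives 54 of 54. It would therefore be too strong to say that no analysis can do it. These models obtain the answer from an assumed shape, and the first relies on small variation in visit timing.

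**Escalation is openly declared, and analysis detail belongs in the SAP.** Escalation suits the tolerability aim in Objective 4, and the protocol states no test or ranking rule. But the protocol itself fixes both the dose order and the wording of Objective 3. An unseen SAP cannot recover the contrast from new entrants without such strong assumptions.

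**Conclusion.** The point holds as a mismatch between Objective 3 and the design, and should be fixed. For new entrants, with free month effects, none of the three dose differences is estimable (54 of 56; 55 of 58). This follows from the fixed order and does not depend on any assumed effect size.

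Rollovers change the answer only through assumptions about month profiles across cohorts. TID rollovers alone must share the new entrants' profile. With both once-daily and TID rollovers, those two groups must share one with each other. With a separate profile for every cohort, no contrast is estimable.

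These assumptions are doubtful because rollovers were selected for completing Study 001, have already taken the drug and reuse an earlier baseline. How many will enrol, and at which doses, is not fixed. The cohort splits used above are assumed. The size of any month effect in this population cannot be derived from the protocol, so the direction and size of the resulting error are unknown.

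**What to change.** - Reword Objective 3 to: *describe BCVA, OCT and tolerability at successive steps of a fixed escalation*.
- Add that results at Visits 2, 3 and 4 are cumulative responses and will not be used to rank doses for benefit.
- Describe new entrants and Study 001 rollovers separately.

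The cost is the wording of one objective and a short added statement. Dosing, visits and data collection stay unchanged. What is given up is a ranking of doses for benefit that this design cannot support.

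### Objectives 1 and 2 ask whether levodopa improves BCVA and OCT, but every patient is injected with anti-VEGF on the first dosing day and nobody is followed without levodopa

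*Protocol*

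**What the plan says.** The protocol describes its design as "Prospective, open-label, escalating dose". Objective 1 reads "To determine whether L-DOPA-carbidopa supplementation can improve visual function, within 30-90 days", assessed by BCVA. Objective 2 asks in the same causal form whether the drug "can improve the anatomic findings on optical coherence tomography (OCT), within 30-90 days".

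The Treatments section sets out one ascending sequence of three monthly dose levels and states: "Each patient will receive an injection of anti-VEGF medication on the day carbidopa-levodopa dosing begins in this study". No placebo, injection-only or untreated group or period is described. Measurements and Activities mentions randomization once, but no arms are attached to it.

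There are three ways in (Inclusion criteria):
- "Not previously treated with anti-VEGF injections"
- "On anti-VEGF injections for at least 3 months, and meets criteria for a repeat injection"
- "Patients, who have completed Study 001, may enter this trial", starting at the dose level they had there.

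The other eye must be "Normal or dry AMD of any grade in the fellow eye". A baseline evaluation already made in Study 001 is carried over (Measurements and Activities). Under Criteria for repeat anti-VEGF injections, later injections depend partly on a five-letter BCVA loss and on OCT thickening, and may be withheld at visits 2-4 if no criterion is met and the patient agrees.

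**The concern.** Levodopa and a fresh anti-VEGF injection start on the same day in every patient. Every BCVA or OCT reading taken after dosing begins in this study follows both. If acuity rises or the macula thins, the data cannot say which treatment, or the mere passage of time, was responsible.

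The objectives nevertheless promise an answer about levodopa specifically. A gain that the injection alone could have produced might be credited to the drug. The section on sharing results commits the study to telling patients about vision-related outcomes, so the attribution would reach them as well.

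The size of any gain would also depend on the mix of entry routes, which the protocol does not fix. Naive patients receive their first injection, treated patients enter when a repeat is due, and Study 001 entrants have already taken the drug.

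**Working it through.** **1. What change from baseline estimates.** For a patient whose baseline is taken in this study, the expected change at a later visit can be written

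mean change = levodopa effect + anti-VEGF effect + time effect.

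Before baseline neither treatment of this study has started. After baseline all patients have had both. The three terms switch on together, so only their sum can be estimated. A larger n makes the sum more precise and does not split it.

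**2. Possible sources of separation inside the trial.**
- *Fellow eye.* It has no neovascular disease, so it cannot stand in for an injected neovascular eye.
- *Dose steps without a new injection.* The dose can rise at visits 2 and 3, so there are at most two such steps per patient. They occur later in time and only in patients judged not to need an injection, so they are confounded with time and selected on outcome.
- *Later injections.* They are triggered partly by BCVA and OCT, the outcomes themselves.
- *Study 001 entrants.* They may start at a higher dose level, but they differ by earlier exposure. Where the Study 001 baseline is reused, their change can span that earlier treatment.

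None of these supplies levodopa-free follow-up of a neovascular eye.

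**3. The stated figure.** The protocol gives 52 completed subjects with no effect size, SD, power or test beside it. The number can be neither reproduced nor refuted, and this point does not rest on it.

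**4. Illustration of size.** From the protocol: n = 52. Assumed: paired t-test, two-sided 5%, SD of BCVA change 8, 10 or 12 letters, levodopa effect zero, background gain m from all other causes.

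The probability of a significant improvement is P(T > t(0.975; 51 df)), where T is noncentral t with 51 df and noncentrality m·√52/SD. For m = 3 and SD = 8 the noncentrality is 3 × 7.211/8 = 2.70, which gives 75.6%.

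| Background gain | SD 8 | SD 10 | SD 12 |
|---|---|---|---|
| 0 letters | 2.5% | 2.5% | 2.5% |
| 2 letters | 42.4% | 29.3% | 21.7% |
| 3 letters | 75.6% | 56.5% | 42.4% |
| 5 letters | 99.3% | 94.3% | 83.8% |

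The smallest mean gain that reaches significance is t·SD/√52 = 2.23, 2.78 or 3.34 letters.

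**5. Precision by entry route.** With an assumed equal split, 52/3 is about 17 per route. The 95% CI half-width t·SD/√17 (16 df) is 4.1, 5.1 or 6.2 letters, against 2.2, 2.8 or 3.3 for all 52.

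**6. Size of a comparator design.** For an assumed 5-letter difference, 80% power and a two-sided 5% two-sample t-test, the need is 42, 64 or 92 patients per arm at SD 8, 10 or 12.

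**The case against.** The strongest reply is that this is a dose-ranging study, openly labelled open-label and escalating, with tolerability and dose comparison among its aims and no claim to be confirmatory. That bears on how serious the point is, but it does not remove it. Objectives 1 and 2 come first, are not marked exploratory, and are worded causally.

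A second reply is that the analysis belongs in a statistical analysis plan, which may exist. That is fair for details such as reporting by entry route. It does not meet the main point, because no analysis plan can recover levodopa-free data that the trial does not collect, and the protocol mentions no external control.

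A third reply stands in full. The protocol names no endpoint contrast, test or success criterion, and nothing in it quantifies the response to one injection, least of all in patients already treated for three months or more. The percentages above therefore describe an assumed test with assumed SDs and gains. They show how easily misattribution could arise and do not predict what this trial will find.

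A reader might also infer that regression to the mean inflates the result by a known amount. The documents do not support that. It could arise only in patients who qualify on a measured worsening and whose qualifying reading is also the baseline, and the protocol does not say whether the two coincide. Patients may also qualify on subjective decline or on the specialist's opinion. For those who do qualify on a measured BCVA drop that is also the baseline, the contribution could lie anywhere from 0 to about 4.6 letters (assumed measurement SD 2-5 letters). It is secondary to the day-one injection.

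**Conclusion.** The point holds. As worded, Objectives 1 and 2 cannot be answered by this design, because the levodopa effect is inseparable from the anti-VEGF and time effects at any sample size. That conclusion follows from the protocol's text alone. Its possible size (42-76% false attribution at a 3-letter background gain, 84-99% at 5 letters) rests on the assumed paired t-test, n = 52 and SD of 8-12 letters.

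Three stronger readings are not supported. Nothing here shows that levodopa is ineffective. It is not true that every dose step comes with an injection, since injections may be withheld at later visits; those steps simply do not rescue the question. Nor is the whole study undermined: tolerability (Objective 4) can be described without a control, and Objectives 3 and 5 lie outside this point.

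**What to change.** Reword Objectives 1 and 2 along these lines: *to describe the change in BCVA and OCT over 30-90 days under combined anti-VEGF and carbidopa-levodopa*, with no claim that levodopa caused it. Report that change separately for anti-VEGF-naive, previously treated and Study 001 entrants, and flag every patient whose baseline is carried over from Study 001. This reporting may sit in the protocol or in the analysis plan.

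The change affects two sentences and three reporting groups. Entry route is known at enrolment, so visits, data collection and sample size stay as they are. The costs are a weaker efficacy claim and subgroup estimates with half-widths of about 4-6 letters at an assumed 17 per route.

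If the sponsor wants to keep the causal question, a concurrent anti-VEGF-only comparator is needed. That is not a cheap change: 42-92 patients per arm under the assumptions shown.
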